10. Female subjects of childbearing potential (FCBP^a) must have a negative serum or urine pregnancy test with a sensitivity of at least 25 mIU/mL within 10 – 14 days and again within 24 hours prior to starting Cycle 1 of pomalidomide. All subjects must be counseled at a minimum of every 28 days about pregnancy precautions and risks of fetal exposure. See [Appendix 8](#) (**for ex-US sites only**).
11. Male subjects must agree to use a latex condom during sexual contact with a FCBP even if they have had a successful vasectomy (**for US/Canada sites only**).
12. Male subjects must agree to use a latex condom during sexual contact with a FCBP even if they have had a successful vasectomy. All subjects must be counseled at a minimum of every 28 days about pregnancy precautions and risks of fetal exposure. See [Appendix 8](#) (**for ex-US sites only**).
13. FCBP^a and male subjects who are sexually active must use TWO acceptable methods of birth control, one highly effective method of birth control plus one additional effective method of birth control for at least 28 days prior to study treatment and during the study treatment period. For female and male subjects, these birth control requirements must be adhered to for 90 days after the last dose of ibrutinib and pomalidomide, whichever is later. Male subjects must agree to not donate sperm during the study treatment period and up to 90 days after the last dose of ibrutinib and pomalidomide, whichever is later.

^a. A female of childbearing potential (FCBP) is a female who: 1) has achieved menarche at some point; or 2) has not undergone a hysterectomy or bilateral oophorectomy; or 3) has not been naturally postmenopausal (amenorrhea following cancer therapy does not rule out childbearing potential) for at least 24 consecutive months (ie, has had menses at any time in the preceding 24 consecutive months).

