11.2.4. Pregnancy

Before study enrollment, subjects must agree to take appropriate measures to avoid pregnancy. However, should a pregnancy occur in a female study subject or a male subject's partner, consent to provide follow-up information regarding the outcome of the pregnancy and the health of the infant until 1 year old will be requested.

A female subject must immediately inform the Investigator if she becomes pregnant from the time of consent to 90 days after the last dose of study drug. A male subject must immediately inform the Investigator if his partner becomes pregnant from the time of his consent to 90 days after the last dose of study drug. Any female subjects receiving study drug(s) who become pregnant must immediately discontinue study treatment. The Investigator should counsel the subject, discussing any risks of continuing the pregnancy and any possible effects on the fetus.

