11.2.4.1. Pregnancy Reporting

Although pregnancy itself is not regarded as an AE, the outcome will need to be documented. Any pregnancy occurring in a subject or subject's partner from the time of first dose up until

90 days after the last dose of study drug must be reported. Any occurrence of pregnancy must be recorded on the Pregnancy Report Form Part I and submitted to Pharmacyclics Drug Safety, or designee, within 24 hours of learning of the event. All pregnancies will be followed for outcome, which is defined as elective termination of the pregnancy, miscarriage, or delivery of the fetus. For pregnancies with an outcome of live birth, the newborn infant will be followed until 1 year old by completing the Pregnancy Report Form Part II. Any congenital anomaly/birth defect noted in the infant must be reported as a SAE.

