Appendix 8. Pomalidomide Pregnancy Prevention Risk Plan (For Ex-US Sites Only)

1. Pomalidomide Pregnancy Prevention Plan for Subjects in Clinical Trials

The Pregnancy Prevention Plan (PPP) applies to all subjects receiving pomalidomide within a clinical trial. The following PPP documents are included:

1. The Pomalidomide Risks of Fetal Exposure, Pregnancy Testing Guidelines and Acceptable Birth Control Methods document (Section 2) provides the following information:
 - Potential risks to the fetus associated with pomalidomide exposure
 - Definition of female of childbearing potential (FCBP)/female not of childbearing potential (FNCP)
 - Requirements for counseling of all subjects receiving pomalidomide about pregnancy precautions and the potential risks of fetal exposure to pomalidomide
 - Acceptable birth control methods for both female subjects of childbearing potential and male subjects receiving pomalidomide in the study
 - Pregnancy testing requirements for subjects receiving pomalidomide who are FCBP
2. The Pomalidomide Education and Counseling Guidance Document for each gender (female and male; [Section 3](#) and [Section 4](#) respectively) must be completed and signed by a trained counselor at the participating clinical center prior to each dispensing of pomalidomide. A copy of this document must be maintained in the subject's records for each dispense.
3. The Pomalidomide Information Sheet [Section 5](#) will be given to each subject receiving pomalidomide. The subject must read this document prior to starting pomalidomide and each time the subject receives a new supply of pomalidomide.

2. Pomalidomide Risks of Fetal Exposure, Pregnancy Testing Guidelines and Acceptable Birth Control Methods

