2.2. Counseling

2.2.1. Females of Childbearing Potential

For a FCBP, pomalidomide is contraindicated unless all of the following are met (ie, all FCBP must be counseled concerning the following risks and requirements prior to the start of pomalidomide):

- She understands the potential teratogenic risk to the unborn child
- She understands the need for effective contraception, without interruption, 28 days before starting pomalidomide, throughout the entire duration of pomalidomide, during dose interruptions and for at least 28 days after the last dose of pomalidomide
- She understands and agrees to inform the Investigator if a change or stop of method of contraception is needed
- She must be capable of complying with effective contraceptive measures
- She is informed and understands the potential consequences of pregnancy and the need to notify her study doctor immediately if there is a risk of pregnancy
- She understands the need to commence pomalidomide as soon as it is dispensed following a negative pregnancy test
- She understands and accepts the need to undergo pregnancy testing based on the frequency outlined in this plan ([Section 2.4](#) of [Appendix 8](#)) and in the Informed Consent
- She acknowledges that she understands the hazards pomalidomide can cause to an unborn fetus and the necessary precautions associated with the use of pomalidomide.

The Investigator must ensure that a FCBP:

- Complies with the conditions of the pregnancy prevention plan, including confirmation that she has an adequate level of understanding
- Acknowledges the aforementioned requirements.

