2.3. Contraception

2.3.1. Female Subjects of Childbearing Potential

Females of childbearing potential enrolled in this protocol must agree to use two reliable forms of contraception simultaneously or to practice complete abstinence (True abstinence is acceptable when this is in line with the preferred and usual lifestyle of the subject. Periodic abstinence [eg calendar, ovulation, symptothermal or post-ovulation methods] and withdrawal are not acceptable methods of contraception.) from heterosexual contact during the following time periods related to this study: 1) for at least 28 days before starting pomalidomide; 2) while taking pomalidomide; 3) during dose interruptions; and 4) for at least 28 days after the last dose of pomalidomide.

The two methods of reliable contraception must include one highly effective method and one additional effective (barrier) method. If the below contraception methods are not appropriate for the FCBP, she must be referred to a qualified provider of contraception methods to determine the medically effective contraception method appropriate to the subject. The following are examples of highly effective and additional effective methods of contraception:

- Examples of highly effective methods:
 - Intra-uterine device (IUD)
 - Hormonal (birth control pills, injections, implants, levonorgestrel-releasing intrauterine system [IUS], medroxyprogesterone acetate depot injections, ovulation inhibitory progesterone-only pills [e.g. desogestrel])

- Tubal ligation
- Partner's vasectomy
- Examples of additional effective methods:
 - Male condom
 - Diaphragm
 - Cervical Cap

Because of the increased risk of venous thromboembolism in subjects with MM taking pomalidomide and dexamethasone, combined oral contraceptive pills are not recommended. If a subject is currently using combined oral contraception the subject should switch to another one of the highly effective methods listed above. The risk of venous thromboembolism continues for 4 to 6 weeks after discontinuing combined oral contraception. The efficacy of contraceptive steroids may be reduced during co-treatment with dexamethasone.

Implants and levonorgestrel-releasing intrauterine systems are associated with an increased risk of infection at the time of insertion and irregular vaginal bleeding. Prophylactic antibiotics should be considered particularly in subjects with neutropenia.

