2.3.2. Male Subjects

Male subjects must practice complete abstinence (True abstinence is acceptable when this is in line with the preferred and usual lifestyle of the subject. Periodic abstinence [eg calendar, ovulation, symptothermal or post-ovulation methods] and withdrawal are not acceptable methods of contraception.) or agree to use a condom during sexual contact with a pregnant female or a FCBP while taking pomalidomide, during dose interruptions and for at least 28 days after the last dose of pomalidomide, even if he has undergone a successful vasectomy.

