2.5. Pregnancy Precautions for Pomalidomide Use

2.5.1. Before Starting Pomalidomide

Female Subjects of Childbearing Potential

Females of childbearing potential must have two negative pregnancy tests (sensitivity of at least 25 mIU/mL) prior to starting pomalidomide. The first pregnancy test must be performed within 10 to 14 days prior to the start of pomalidomide and the second pregnancy test must be performed within 24 hours prior to the start of pomalidomide. The subject may not receive pomalidomide until the study doctor has verified that the results of these pregnancy tests are negative.

Females of childbearing potential must use two reliable forms of contraception simultaneously, or practice complete abstinence (True abstinence is acceptable when this is in line with the preferred and usual lifestyle of the subject. Periodic abstinence [eg calendar, ovulation, symptothermal or post-ovulation methods] and withdrawal are not acceptable methods of contraception.) from heterosexual contact for at least 28 days before starting pomalidomide.

Male Subjects

Male subjects must agree to practice complete abstinence (True abstinence is acceptable when this is in line with the preferred and usual lifestyle of the subject. Periodic abstinence [eg calendar, ovulation, symptothermal or post-ovulation methods] and withdrawal are not acceptable methods of contraception.) or agree to use a condom during sexual contact with a pregnant female or a FCBP while taking pomalidomide, during dose interruptions and for at least 28 days after the last dose of pomalidomide, even if he has undergone a successful vasectomy.

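### The ex-US pomalidomide plan and its counseling forms state a 28-day minimum after pomalidomide for contraception and semen donation, while criterion 13 requires 90 days after the later of ibrutinib or pomalidomide.

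*Protocol*

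**What the plan says.** **The study-level rule.** Protocol Section 4.1, criterion 13 (repeated in the Synopsis) asks sexually active men and women of childbearing potential for one highly effective and one additional contraceptive method. After treatment, "these birth control requirements must be adhered to for 90 days after the last dose of ibrutinib and pomalidomide, whichever is later". The sperm-donation ban runs to the same point. Criteria 8 to 12 are each limited to US/Canada or ex-US sites; criterion 13 is not.

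The safety sections match it. Section 11.2.4 requires a man to tell the investigator "if his partner becomes pregnant from the time of his consent to 90 days after the last dose of study drug", and has a parallel duty for women. Section 11.2.4.1 says that a pregnancy up to "90 days after the last dose of study drug must be reported".

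**The ex-US plan.** Appendix 8 applies to ex-US sites only. Its education and counseling form "must be completed and signed by a trained counselor at the participating clinical center prior to each dispensing of pomalidomide". Section 5.5.3 withholds drug until that step is done and also requires counseling when pomalidomide is discontinued.

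The post-treatment period in Appendix 8 is different:

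- Section 2.2.1 (women): contraception "throughout the entire duration of pomalidomide, during dose interruptions and for at least 28 days after the last dose of pomalidomide".
- Section 2.3.1 (women): "during dose interruptions; and 4) for at least 28 days after the last dose of pomalidomide".
- Section 2.3.2 (men): condom or abstinence "for at least 28 days after the last dose of pomalidomide, even if he has undergone a successful vasectomy".
- Section 2.5.1 (men): abstain "or agree to use a condom during sexual contact with a pregnant female or a FCBP while taking pomalidomide, during dose interruptions", followed by the same 28 days.

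Section 2.5.2 and forms 3.1 (women) and 4 (men) carry the same 28-day period. Section 2.5.2 and form 4 apply it to semen donation as well.

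**The concern.** Criterion 13 is agreed to at enrolment, but the obligation bites after treatment ends. What an ex-US subject is told nearer that time comes from Appendix 8, because the form is completed at each dispensing and counseling is repeated at pomalidomide discontinuation. That text gives a shorter minimum, starts the clock from one of the two drugs, and asks men for less than criterion 13 does.

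The starting point matters because pomalidomide is not the only teratogenic risk in the regimen. Protocol Section 1.2.1.2 reports malformations in rats and rabbits at roughly 14 and 2 times the human exposure at 560 mg of ibrutinib. A subject who stopped contraception on the form's stated minimum would do so inside the period that the protocol itself treats as at risk and for which it still requires pregnancies to be reported.

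No endpoint, estimate or error rate is involved. The stake is subject safety and a consistent instruction.

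**Working it through.** The plan gives no figure to reproduce, so the check compares the texts and does one subtraction.

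**Step 1. The two rules as end dates.** Let P be the last pomalidomide day and I the last ibrutinib (or placebo) day.

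- Criterion 13: end = later of (I, P) + 90 days.
- Appendix 8: minimum end = P + 28 days.
- Shortfall = (90 − 28) + (days by which I falls after P, or 0 if it does not).

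**Step 2. Both drugs stop together (I = P).** Shortfall = 90 − 28 = **62 days**. The stated minimum is 28/90 = 31% of the required period.

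**Step 3. Effect of the starting point.** Ibrutinib is taken daily, and pomalidomide on Days 1 to 21 of a 28-day cycle. A subject whose last cycle is taken in full ends pomalidomide on Day 21 and ibrutinib on Day 28, so I − P = 7 and the shortfall is 62 + 7 = 69 days. It grows further if ibrutinib continues after pomalidomide is stopped for good. That such continuation is allowed is an inference: Sections 5.4.4 and 9.2 tie the end of treatment to ibrutinib or placebo, and Section 5.6.2 states continuation only for dexamethasone. The conclusion does not rest on it.

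**Step 4. Where the 28-day period appears in Appendix 8.** Only post-treatment contraception and semen-donation statements are counted.

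| Place | Rule | Statements |
|---|---|---|
| 2.2.1 | female contraception | 1 |
| 2.3.1 | female contraception | 1 |
| Form 3.1 | female contraception | 1 |
| 2.3.2 | male condom or abstinence | 1 |
| 2.5.1 | male condom or abstinence | 1 |
| 2.5.2 | male condom or abstinence; semen donation | 2 |
| Form 4 | male condom or abstinence; semen donation | 2 |

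Total: 3 female + 4 male + 2 semen = 9. None counts from ibrutinib or gives 90 days, and the readable text of Appendix 8 never names ibrutinib. The 28-day breastfeeding and blood-donation rules are left out because criterion 13 does not cover them.

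**Step 5. Content for men.** Criterion 13: two methods. Appendix 8: condom or abstinence, and only for contact with a pregnant woman or a woman of childbearing potential.

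**Step 6. Who is exposed.** SAP Section 1 says 11 subjects were treated in Phase 1, and Section 6 says Phase 2 was not started. Neither document says how many of the 11, if any, were at ex-US sites.

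**The case against.** The strongest defence is that nothing conflicts. Appendix 8 always sets a minimum, so a subject who follows criterion 13 meets both texts, and criterion 13 binds ex-US subjects as a condition of entry. That stands: a reader might infer that the protocol contradicts itself, or that ex-US subjects owe only 28 days, and the documents support neither.

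Appendix 8 is also a pomalidomide plan, so its silence on ibrutinib is unsurprising, and the nine statements are largely one template sentence repeated. Both points are fair; the count shows how many places need editing, not nine defects. But criteria 10 and 12 send ex-US sites to this appendix for this combination, and the counselor works from its forms.

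The Pomalidomide Information Sheet and the consent pages could not be read and may give 90 days. So it cannot be said that any subject would hear only the shorter period.

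Three wider readings also go too far:

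- That the male wording affects every sexually active ex-US man. The condom rule covers only the contacts named in Step 5, and semen donation does not depend on sexual activity.
- That the pregnancy-testing schedule has the same gap, because the Appendix 1 row sets no drug limit on periodic tests. Footnote v to that row limits them to pomalidomide therapy, as do Sections 5.5.3 and 7.3.7. Testing throughout ibrutinib-only treatment would be a new rule.
- That counseling frequency is inconsistent. Criteria 10 and 12 point to Appendix 8, whose counseling rule sits under precautions for pomalidomide use, so there is no clear mismatch with Section 5.5.3.

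**Conclusion.** The concern holds as a minor point. The ex-US plan and its forms state a shorter minimum that is not reconciled with the protocol's own rule: 62 days shorter when both drugs stop together, counted from pomalidomide only, and with a lighter requirement for men.

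This rests on criterion 13 applying at all sites, which its lack of a site limit supports, and on the readable part of Appendix 8. Practical harm is not shown. The number of ex-US subjects affected is unknown and may be zero among the 11 treated, and the unseen Information Sheet may already give the longer period. The point matters mainly as a text correction, including wherever these forms might be reused.

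**What to change.** In Appendix 8 Sections 2.2.1, 2.3.1, 2.3.2, 2.5.1 and 2.5.2, and in forms 3.1 and 4, replace the post-treatment period for contraception and semen donation with: *90 days after the last dose of ibrutinib/placebo or pomalidomide, whichever is later.* Bring the male contraception wording into line with criterion 13.

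If the forms are a manufacturer's template that cannot be edited, attach a one-sentence study-specific addendum that states the 90-day period and cites criterion 13. Leave the 28-day breastfeeding and blood-donation rules unchanged, and check that the Information Sheet and consent form agree.

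The cost is wording plus re-approval of the forms. The pomalidomide manufacturer's agreement may also be needed. That is an assumption, but a reasonable one: Section 5.5.3 has the manufacturer train the counselors, and Section 7.3.7 follows its pregnancy prevention guidelines. No extra visits, tests or data are required.

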4.1.1. Inclusion Criteria for Open-label Sub-study Arm C (Phase 2b)

To be enrolled in the sub-study, each potential subject must meet all inclusion criteria defined in [Section 4.1](#). IN ADDITION the following criteria must be met:

Subject must have received pomalidomide in combination with dexamethasone (regimen must not have included other anti-cancer agents) as their most recent line of therapy and have:

- Achieved less than a partial response (<PR) following at least 112 days (4 x 28 day cycles) and are without evidence of progression disease (PD)
OR
- Disease progression following an initial confirmed response of MR or better to the combination (according to IMWG response criteria; [Rajkumar 2011](#))

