2.4. Open-Label Sub-Study Treatment Arm C (Phase 2b)

- To evaluate the efficacy and safety of ibrutinib in combination with pomalidomide and dexamethasone in subjects who either have:
 - Less than a partial response ($<$ PR) following at least 112 days (4 x 28 day cycles) of pomalidomide and dexamethasone (regimen must not have included other anti-cancer agents) and are without evidence of disease progression

OR

- o Disease progression following an initial confirmed response of MR or better to the combination of pomalidomide and dexamethasone (regimen must not have included other anti-cancer agents)

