4.1. Inclusion Criteria

To be enrolled in the study, each potential subject must meet all of the following inclusion criteria.

Disease Related

1. Subjects with relapsed/refractory MM who have received at least two prior lines of therapy ([Appendix 4](#)) including lenalidomide (LEN) and either bortezomib or carfilzomib and have demonstrated disease progression on or within 60 days of the completion of the most recent treatment regimen.
 - Subjects must have received at least 2 cycles of treatment with LEN and either bortezomib or carfilzomib at the approved dose and schedule (maintenance will be excluded).
2. Measurable disease defined by at least ONE of the following:
 - Serum monoclonal protein (SPEP) ≥ 1 g/dL.
 - Urine monoclonal protein (UPEP) ≥ 200 mg by 24 hour urine.

Laboratory

3. Adequate hematologic function independent of platelet transfusion and growth factor support for at least 7 days prior to Screening and dosing (Phase 1) or randomization/enrollment (Phase 2b), with the exception of pegylated G-CSF (granulocyte-colony stimulating factor pegfilgrastim) and darbopoeitin which require at least 14 days, defined as:
 - Absolute neutrophil count ≥ 1500 cells/mm³ (1.5×10^9 /L).
 - Platelet count $> 75,000$ cells/mm³ (75×10^9 /L).
 - Hemoglobin ≥ 8.0 g/dL.
4. Adequate hepatic and renal function defined as:
 - Serum aspartate transaminase (AST) or alanine transaminase (ALT) ≤ 3.0 x upper limit of normal (ULN).

- Serum creatinine < 3.0 mg/dL AND Creatinine Clearance ≥ 30 mL/min (by Cockcroft-Gault estimation OR as measured by 24 hour urine collection).
 - Total Bilirubin ≤ 2.0 mg/dL (unless bilirubin rise is due to Gilbert's syndrome or of non-hepatic origin).
5. PT/INR ≤ 1.5 x ULN and PTT (aPTT) ≤ 1.5 x ULN (unless on warfarin, then INR ≤ 3.0).

Demographic

6. Men and women ≥ 18 years of age.
7. Eastern Cooperative Oncology Group (ECOG) performance status of ≤ 2

Ethical/Other

8. All study participants must be registered into the mandatory Pomalyst REMS™ program or RevAid® program, and be willing and able to comply with the requirements of the Pomalyst REMS™ program or RevAid® program as appropriate for the country in which the drug is being used (**for US/Canada sites only**).
9. Female subjects of childbearing potential (FCBP^a) must adhere to the scheduled pregnancy testing as required in the Pomalyst REMS™ program or RevAid® program as appropriate for the country in which the drug is being used. (**for US/Canada sites only**).

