4.2.1. Exclusion Criteria for Open-Label Sub-Study Arm C (Phase 2b)

To be enrolled in the sub-study, each potential subject must not meet any exclusion criteria defined in [Section 4.2](#) EXCEPT for exclusion criteria 5 which is related to prior pomalidomide and does not apply for the sub-study Arm C.

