Appendix 4. Lines of Therapy

According to the IMWG Consensus panel on uniform reporting criteria in clinical trials ([Rajkumar 2011](#)), a line of therapy consists of at least 1 or more cycles of a planned treatment regimen. This may consist of single-agent or combination therapy or a sequence of treatments administered in a planned manner. For example, a planned induction, followed by autologous stem cell transplant (ASCT) followed by maintenance is considered one line of therapy. A new line of therapy starts when a planned course is modified as a result of progression, relapse or toxicity or when a planned period of observation is interrupted by the need for additional treatment of the disease. Modification of drug doses or resuming therapy after holding will not be considered a new line of therapy provided that there was no evidence of progression of disease as defined in the “Response Criteria” section of this document.

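### Arm C's first target group must be free of progression on pomalidomide-dexamethasone, yet an inclusion criterion that also applies to Arm C requires progression on or shortly after that regimen, so the group cannot be enrolled as written.

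*Protocol*

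**What the plan says.** The Arm C objective (Protocol Section 2.4, repeated in the synopsis) names two populations. The first has less than a partial response after at least four 28-day cycles of pomalidomide-dexamethasone, in subjects who "are without evidence of disease progression". The second progressed after a confirmed minimal response or better to the same combination.

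Section 4.1.1 turns this into eligibility rules in three steps:

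- For Arm C, "each potential subject must meet all inclusion criteria defined in" Section 4.1, with the sub-study criteria added on top.
- Pomalidomide-dexamethasone, without other anti-cancer agents, must have been received "as their most recent line of therapy and have" one of two outcomes.
- The first outcome is less than a partial response "following at least 112 days (4 x 28 day cycles) and are without evidence of progression disease (PD"). The second is progression after a minimal response or better.

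Criterion 1 of Section 4.1 requires that subjects have "demonstrated disease progression on or within 60 days of the completion of the most recent treatment regimen".

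Section 4.2.1 applies all the exclusion criteria to Arm C "EXCEPT for exclusion criteria 5 which is related to prior pomalidomide and does not apply for the sub-study Arm C". It is the only exception written for the sub-study.

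**The concern.** The text adds the Arm C criteria to the general ones and does not replace them, so a first-group subject has to satisfy both. Criterion 1 asks for progression on or soon after the most recent regimen. For Arm C that regimen is pomalidomide-dexamethasone, and the first group is defined by not having progressed on it.

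If the rules are followed, Arm C enrols nobody from a population its objective names, and the response-rate test describes only subjects who progressed after an initial response. If sites follow the evident intent instead, every first-group subject enters as an eligibility deviation.

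**Working it through.** **Do the criteria conflict?** This part is logic and needs no arithmetic.

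1. *Which regimen does criterion 1 refer to?* Section 4.1.1 makes pomalidomide-dexamethasone the most recent line. Criterion 1 speaks of a regimen, but Appendix 4 says "a line of therapy consists of at least 1 or more cycles of a planned treatment regimen". A line can contain a planned sequence of treatments, but Section 4.1.1 rules out other anti-cancer agents in this regimen. Both terms point to the same treatment.
2. *Apply both rules to each group.*

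| Arm C group | Status required by 4.1.1 | Status required by 4.1, criterion 1 | Compatible? |
|---|---|---|---|
| First | Less than PR after at least 112 days, no PD | PD on, or within 60 days of completing, the regimen | No |
| Second | PD after MR or better | Same | Yes, if the PD falls in that window |

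3. *Is there an exception elsewhere?* Section 4.2.1 waives exclusion 5 only. Section 3 repeats the progression requirement when it describes screening and makes no exception for Arm C. Section 8.3 allows Arm C enrolment only when the Section 4 criteria are satisfied.

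**Is the Arm C sample size affected?** Inputs from Section 10.2: n = 22, null response rate 5%, alternative 18%, one-sided level 0.1, exact binomial test. With success declared at r or more responders, the rejection probability is P(X ≥ r) = 1 − Σ C(22,k) pᵏ (1−p)²²⁻ᵏ, summed over k = 0 to r − 1.

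| r | Alpha (p = 0.05) | Power (p = 0.18) |
|---|---|---|
| 2 | 0.3018 | 0.9260 |
| 3 | 0.0948 | 0.7846 |
| 4 | 0.0222 | 0.5776 |

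The smallest cut-off with alpha at or below 0.1 is r = 3. Its power of 78.5% reproduces the protocol's 78%, and it stays the same if all 22 subjects come from the second group.

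**If first-group places stayed unfilled.** The documents give no expected split between the groups, so these sizes are assumptions for illustration. The smallest cut-off with alpha at or below 0.1 is again 3 responders in each case, and power is 72.5% at n = 20, 57.0% at n = 16 and 31.6% at n = 11.

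**The case against.** The best counter-argument uses the full wording of criterion 1, which accepts progression up to 60 days after the regimen is completed. A subject could have less than a partial response and no progression after 112 days, stop treatment, and then progress within 60 days. If the first outcome describes status at the earlier point, that subject meets both rules. The reading is possible but weak. Both Section 2.4 and Section 4.1.1 put the absence of progression in the present tense, and a subject who has since progressed is no longer in the group the objective describes.

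A second argument is that the intent is plain. Section 8.3 describes Arm C candidates as refractory to pomalidomide-dexamethasone and points to Sections 4.1.1 and 4.2.1, so this looks like a forgotten carve-out. Section 4 sends entry-criteria questions to the Medical Monitor, and Section 7.1.2 requires an approved eligibility worksheet, so the conflict would probably surface at the first candidate. That is fair, and it makes unnoticed misuse less likely. Neither step amends the criteria, though, and Section 7.1.2 also requires documentation that all inclusion criteria are met.

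Third, Arm C is a small, uncontrolled sub-study outside the randomized PFS comparison and its interim analyses. That stands: the conflict does not touch the primary endpoint or its type I error.

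**Conclusion.** The concern holds. On the plain reading the first Arm C group has no eligible members, so up to 22 of 22 subjects would come from the second group. That figure is a logical bound and not a forecast of enrolment. The conclusion assumes that the first group's freedom from progression applies at study entry, as the present tense indicates, and that line and regimen mean the same treatment here.

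The Arm C design figures are correct. What fails is the match between the objective and the population that can enter. This is an internal contradiction that needed resolving before Arm C opened. The practical urgency is now low: the SAP (Introduction and Section 6) covers Phase 1 only and records that Phase 2b was not initiated.

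**What to change.** The sponsor should reconcile the passages in one of two ways:

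- State in Section 4.1.1 that the progression clause of inclusion criterion 1 does not apply to the first group, in the way Section 4.2.1 already handles exclusion 5.
- Remove the first group from the synopsis, Section 2.4 and Section 4.1.1.

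Which population Arm C should study is the sponsor's decision. If the group is kept, the progression requirement in the synopsis inclusion criteria and in the screening text of Section 3 needs the same exception. Showing the response rate for each group beside the pooled test would be a useful but optional addition; with 22 subjects in all, the separate estimates would be imprecise.

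The cost is one sentence plus conforming edits, or a few deletions. No patients or procedures are added and the sample size does not change. The correction is worth making before this text is reused in another protocol.
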